### Criteria for terminating the study

As the study involves only a single assessment and does not involve investigational medicinal products or medical devices it is not envisaged that circumstances will arise that require termination of this study.

### Transport and Storage of the Tissues

The samples will be stored at University of Nottingham premises. Whole blood (5ml) samples will be stored in a refrigerator (at -20°C) within the Clinical Sciences Building. Remaining blood (5ml) will be centrifuged as soon after venesection as possible and the serum stored, with the urine, at -80C within freezers in University of Nottingham premises at the Clinical Sciences Building (CSB), City Hospital for future biochemical and molecular studies. Excess samples (DNA, serum, saliva, urine and faeces) that remain after the study analyses have been undertaken will remain stored within the CSB for possible future research studies related to OA and/or pain provided that participants are agreeable and sign the optional clause on the consent form. These CSB facilities come within the remit of the Research Tissue Bank (DI [name] Licence Number 12265). Where participants do not agree to the future use of the samples, any samples remaining after the analysis will be destroyed in accordance with the Human Tissue Act, 2004 and GDPR.

Samples will be stored in the linked anonymised format in the CSB and labelled using a randomly generated unique participant identifier to permit accurate linkage to clinical data and the consent form. The master database will be held by the CI in an encrypted password file. After 7 years all personal data linked to the samples will be destroyed.

### **Laboratory Analysis**

Whole blood may be sent to a specialist company for total genomic DNA extraction and processing using standard protocols. The DNA will be used to identify genes that identify with pain progression and severity. Bacterial DNA will be extracted from faecal samples to identify bacterial lineages associated with pain and inflammation. Cortisol will be extracted from saliva samples. Protein and inflammatory markers will be extracted from urine samples. Faecal samples will be stored until all samples are collected (as this is optional) and then they will be sent to the laboratory. Similarly, biochemical/biomarker analyses may be undertaken by other academic or commercial groups. Such investigations will be undertaken on anonymised samples under usual Material Transfer Agreement arrangements. The study will be registered with the Human Tissue Management Group of the UoN. Storage of these tissues will be managed, transported and handled according to Standard Operating Procedure (SOP) HTMG 004. All shipments will contain a complete inventory of all samples, along with the name of the person responsible for sending the samples. Companies which will be used for the analysis should process the samples within seven days upon receipt or companies with HTA licence will be considered. It is anticipated that samples will be destroyed following analysis. There is no plan for long-term storage of such samples by those companies and no samples are expected to be transported back to UoN.

### **Missed Appointments**

Missed appointments are an avoidable cost and resource inefficiency which impacts upon research outcomes. Health care service colleagues are increasingly utilising reminder systems to manage these negative effects. A systematic review (145) found consistent evidence that all types of reminder systems are effective at improving appointment attendance across a range of care settings and patient populations. Therefore, a reminder mechanism (a reminder telephone call, a polite reminder e-mail and where the participant has provided their mobile telephone number, a reminder text message) will be considered.

## **STATISTICS**

### **Methods**

The chief investigator, co-investigators and the study statistician will evaluate the findings and analysis will be carried out by the co-investigator. The data will be entered into MS Access and analysed using with STATA, SPSS (Statistical Packages for Social Scientists, version 19) and R software. Data will allow exploration of potential relationships between objective sensory measures and molecular findings and/or pain. Several factors that putatively mediate the primary or secondary outcomes are inter-correlated so investigation of their interaction must be ascertained. Simple univariate unadjusted correlations (Pearson/Spearman) and linear regression modelling will be used to examine associations between pain and molecular findings in the synovial fluids at baseline. Multiple linear

regression (MLR) modelling (backward stepwise regression) will be conducted to assess the impact of the significant independent variables and their interactions with the dependent variable.

The results of the study will be available to the study management group. All data will be stored in Academic Rheumatology and will be backed up on the University of Nottingham servers.

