Statistical methods	Standard parametric regression methods will be used to assess the levels of association between proteomic profiles, pain and inflammatory markers on ultrasound.

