### **PRIMARY OBJECTIVE**

1. To identify proteomic signatures in synovial fluid of the knee joint in individuals with knee pain.

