### **SECONDARY OBJECTIVES**

1. To test whether there is an association between proteomic concentrations in the synovial fluid and pain.
2. To link the changes in pain and physical activity to biomarkers of insulin resistance, stress, poor metabolism, inflammation and pain.
3. To investigate the relationship of pain and different proteomic profiles with radiologically-established joint structural changes and muscle strength.
4. To explore the correlation between knee inflammation (effusion, synovial hypertrophy or/and synovial hyper vascular), biomarkers of insulin resistance, DNA markers, stress, poor metabolism, gene expression and knee pain.

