### **Sample size and justification**

We propose to compare proteomic signatures in 140 knee pain cases. To achieve a Bonferroni  $p < 1.25 \times 10^{-5}$  (adjusting for 4000 tests, i.e. the number of proteins in the Somalogic platform) effect sizes of beta = 0.64 in units of standard deviations are needed to achieve 80% statistical power. Based on the effects seen on radiographic progression (standardized beta = 0.62) these effects appear reasonable and achievable with the proposed sample size.

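### The multi-protein model is selected and fitted in the same 140 people with no internal validation, so its coefficients and R² would be too optimistic if it is used as the proteomic signature

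*Combined protocol and SAP*

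**What the plan says.** The primary objective is "To identify proteomic signatures in synovial fluid of the knee joint in individuals with knee pain". The first secondary objective is "To test whether there is an association between proteomic concentrations in the synovial fluid and pain".

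The analysis is described under STATISTICS, Methods. The opening step is one molecule at a time: "Simple univariate unadjusted correlations (Pearson/Spearman) and linear regression modelling will be used to examine associations between pain and molecular findings". The next step is multivariable: "regression (MLR) modelling (backward stepwise regression) will be conducted to assess the impact of the significant independent variables and their interactions with the dependent variable". Methods does not define significance, gives no level for staying in the model, and does not say how the fit of the final model will be reported or checked. The SYNOPSIS adds only this: "Standard parametric regression methods will be used to assess the levels of association between proteomic profiles, pain and inflammatory markers on ultrasound".

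A significance level appears in one context, the sample-size text (SYNOPSIS, and Sample size and justification). It is p < 1.25 × 10⁻⁵, explained as "adjusting for 4000 tests, i.e. the number of proteins in the Somalogic platform".

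No section plans a hold-out set, cross-validation, bootstrap or replication cohort. The validation mentioned under Study Data concerns data handling. The 25-person sub-study measures reliability in a subset of the same participants.

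**The concern.** The natural reading of Methods is a two-stage procedure: test each molecule against pain, then put those that were significant into backward elimination. Both stages use the same 140 people. A protein whose sample correlation happens to be high is more likely to pass, and the fitted model then counts that excess as explained variation. The final R², coefficients and p-values take no account of the selection.

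This matters because stepwise regression is the only multivariable method named, and the primary objective is to identify a signature. The plan does not say whether the signature is this model or the list of proteins that pass the Bonferroni level. If it is the model, a reader would take its R² as a measure of how well the signature explains pain, and that figure would be too high by an unknown amount.

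**Working it through.** **Inputs from the documents.** n = 140; 4000 protein tests; level 1.25 × 10⁻⁵; reference standardized beta 0.62 (Sample size and justification). **Assumed, because the plan gives no figure:** two-sided tests; proteins in 20 blocks of 200 with correlation 0.3 within a block; stay level 0.05; the true effects shown below; 0.62 read as a correlation.

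**1. The plan's level.** 0.05 / 4000 = 1.25 × 10⁻⁵, as stated.

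**2. False entry at that level.** For independent tests, 1 − (1 − 1.25 × 10⁻⁵)⁴⁰⁰⁰ = 4.9%. The expected number of null proteins entering is 4000 × 1.25 × 10⁻⁵ = 0.05. Simulated null data (400 data sets per structure) gave at least one entry in 2.5% with independent proteins and 6.5% with the block structure. With one common factor it was 0.5% to 3.5%. A separate run of 200 data sets gave 6.0% with independent proteins. Entry by chance is controlled.

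**3. What a protein must show to enter.** With 138 degrees of freedom the critical value is |r| = t / √(t² + 138) = 0.360, so R² = 0.360² = 0.130. Any protein with a true correlation below 0.360 that passes must therefore be overstated in the sample. For a single protein taken alone (60,000 draws):

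| True r | Passes | True R² | Mean R² if it passes | Ratio |
|---|---|---|---|---|
| 0.3 | 21.8% | 0.090 | 0.162 | 1.8 |
| 0.4 | 71.3% | 0.160 | 0.190 | 1.2 |
| 0.5 | 97.8% | 0.250 | 0.256 | 1.02 |
| 0.62 | 100% | 0.384 | 0.385 | 1.00 |

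For one strong protein the bias is negligible. For modest effects it is not.

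**4. The whole procedure.** This was one-at-a-time tests at 1.25 × 10⁻⁵, then backward elimination, in 200 data sets. R² in new people was computed from the known covariance, and means are over data sets in which something was selected.

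- *Five true proteins at r = 0.3* (true R² 5 × 0.09 = 0.45). Something was selected in 80.5% of data sets, with 1.9 proteins kept on average. Apparent R² was 0.251 against 0.072 in new people. Repeat runs with separately written code gave 0.25 to 0.28 against 0.085 to 0.09. The overstatement is roughly threefold (0.251 / 0.072 = 3.5; 0.28 / 0.09 = 3.1).
- *One true protein at r = 0.62* (true R² 0.384). Something was always selected, with 1.8 proteins kept on average. Apparent R² was 0.411 against 0.348. Repeat runs gave 0.41 to 0.42 against 0.35 to 0.36. The gap of about 0.06 exceeds that in step 3 because proteins in the same block inherit a correlation with pain of about 0.3 × 0.62 = 0.19, and some enter alongside the true one.

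**The case against.** The strongest reply is that the plan describes an exploratory, cross-sectional study. Methods speaks of assessing the impact of variables, and the SYNOPSIS of levels of association. No section promises a predictive model or an R² for use in new patients. This stands in part. The harm arises only if the stepwise model is offered as the signature and its naive fit is reported as performance. The documents leave that open, and the primary objective makes it likely enough to settle in advance.

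It can also be said that Methods never mentions screening, and that the variables entering the regression might include clinical or ultrasound measures. That is fair. The two-stage reading is the natural one but is not explicit.

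A reader might infer three stronger points, which the documents do not support.

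- *That proteins enter at a nominal level such as 0.05, flooding the model with noise.* No such level appears anywhere. The only level given is 1.25 × 10⁻⁵, and it is tied to the number of protein tests.
- *That so many proteins will pass that 140 people cannot support the starting model.* At 1.25 × 10⁻⁵ this was frequent in simulation only when hundreds of proteins (200 to 800 were tried) followed pain through one shared factor. No section describes such a factor. The sentence "Several factors that putatively mediate the primary or secondary outcomes are inter-correlated so investigation of their interaction must be ascertained" concerns putative mediators and does not mention proteins.
- *That stepwise regression must be replaced by penalised regression.* In a small check (25 data sets per setting), lasso did better for five proteins at r = 0.3 (0.20 against 0.07 in new people) but slightly worse for one protein at 0.62 (0.32 against 0.35). The defect is the missing validation, and stepwise regression can be validated.

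**Conclusion.** The concern holds as a cheap improvement. The single-protein tests are sound if they are declared at 1.25 × 10⁻⁵, and chance entry is then held near 5%. Any multi-protein model built as described would report coefficients and an R² that are too optimistic. Under the assumed settings the overstatement is about threefold for several modest proteins (0.25 to 0.28 against 0.07 to 0.09) and small for one strong protein (about 0.41 against 0.35).

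The direction of the bias follows from selecting and fitting in the same data. Its size depends on the assumed block correlation, stay level and true effects, none of which the plan gives. The plan's sample-size text expects strong effects ("Based on the effects seen on radiographic progression (standardized beta = 0.62) these effects appear reasonable and achievable with the proposed sample size"). If that figure can be read as a correlation with pain, the study would sit at the mild end. The figure refers to radiographic progression rather than pain, so the mild case cannot be taken for granted.

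**What to change.** Two additions to Methods:

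1. State that single-protein tests against pain are declared at two-sided p < 1.25 × 10⁻⁵, in line with the sample-size text.
2. For any multi-protein model, state the level for staying in the model. Repeat the whole procedure (one-at-a-time tests, selection and any interaction terms) inside cross-validation or bootstrap resampling. Report the optimism-corrected R² and how often each protein is selected. Do not present the naive stepwise p-values or R² as the signature's performance.

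Lasso or elastic net tuned inside nested cross-validation is a suitable alternative to stepwise selection but is not required.

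The cost is a few sentences and a little more code, with no extra participants, samples or visits. The reported R² will be lower, and at n = 140 cross-validated figures may err low. In the small lasso check, nested cross-validation gave 0.11 where the model explained 0.20 in new people, and 0.29 where it explained 0.32.

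### Backward stepwise selection is applied to interactions with no error level for them; if all pairs enter, about 40–49% of analyses with five variables would keep a false interaction at p<0.05, and more than half from six

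*Combined protocol and SAP*

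**What the plan says.** The analysis is described in the combined protocol and SAP, Statistics, Methods. It begins with a screen: "Simple univariate unadjusted correlations (Pearson/Spearman) and linear regression modelling will be used to examine associations" between pain and the synovial fluid findings. A multivariable step follows: "regression (MLR) modelling (backward stepwise regression) will be conducted" "to assess the impact of the significant independent variables and their interactions with the dependent variable". Earlier in the section the motive is given: "Several factors that putatively mediate the primary or secondary outcomes are inter-correlated so investigation of their interaction must be ascertained".

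The section does not state the level at which a variable counts as significant, the level at which a term stays in the model, how many variables may enter, or which interactions are meant.

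The only error level is in Sample size and justification. It is a Bonferroni level of 1.25 × 10⁻⁵, described as "adjusting for 4000 tests, i.e. the number of proteins in the Somalogic platform". The sample is given there too: "We propose to compare proteomic signatures in 140 knee pain cases".

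**The concern.** With k variables there are k(k−1)/2 pairwise interactions, so the candidate terms grow much faster than the variables. Backward elimination judges each one at its retention level, and nothing in the plan controls the error over the whole set. The Bonferroni level does not help, because it counts proteins one at a time. Even if every variable had passed 1.25 × 10⁻⁵ as a main effect, its products with the others would be new tests that no count includes.

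The final sentence also cannot be carried out literally. It has the interactions running with the dependent variable, whereas in a regression model interactions are between predictors. Two analysts could fit different models from it.

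At stake is the credibility of the only multivariable analysis described in Methods. It could report interactions related to pain that do not exist, and nothing labels them as exploratory results.

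**Working it through.** **Inputs from the plan.** N = 140 and error level 1.25 × 10⁻⁵ for 4000 tests (Sample size and justification); backward stepwise regression with interactions (Methods).

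**Inputs assumed.** All pairwise interactions enter. The number of variables k and the retention level a are not given, so both are varied: a = 0.01, 0.05 and 0.10.

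**Step 1, the plan's error level.** 0.05 / 4000 = 1.25 × 10⁻⁵. It reproduces exactly, and all 4000 units are used by single proteins. The power statement in the same section is not needed here.

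**Step 2, size of the starting model.** Let m = k(k−1)/2 be the number of pairs. Parameters = 1 + k + m.

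**Step 3, false interactions by formula.** If no interaction is real and the tests are treated as independent, P(at least one kept) = 1 − (1 − a)^m.

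| k | m | Parameters | Residual df, N = 140 | a = 0.01 | a = 0.05 | a = 0.10 |
|---|---|---|---|---|---|---|
| 3 | 3 | 7 | 133 | 3.0% | 14.3% | 27.1% |
| 5 | 10 | 16 | 124 | 9.6% | 40.1% | 65.1% |
| 6 | 15 | 22 | 118 | 14.0% | 53.7% | 79.4% |
| 8 | 28 | 37 | 103 | 24.5% | 76.2% | 94.8% |
| 10 | 45 | 56 | 84 | 36.4% | 90.1% | 99.1% |

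For example, at k = 5 and a = 0.05: 1 − 0.95¹⁰ = 0.401.

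**Step 4, false interactions by simulation.** The formula ignores the search itself, so backward elimination was simulated. Settings were 140 people, real main effects, no real interaction, predictor correlations from 0 to 0.5, and versions with and without a rule that parent main effects must stay. With 300 to 400 runs per setting, the simulation error is about 2.5 to 3 percentage points. The share of studies keeping at least one false interaction was:

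- 5 variables: about 9–15% at 0.01, 40–49% at 0.05, 61–73% at 0.10.
- 6 variables: about 53–69% at 0.05, 80–86% at 0.10.
- 8 variables: about 76–90% at 0.05.

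Requiring parent main effects to stay does not remove the problem.

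**Step 5, the limit of fit.**

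- k = 16: 1 + 16 + 120 = 137 parameters, leaving 3 residual degrees of freedom.
- k = 17: 1 + 17 + 136 = 154, more than 140, so the model cannot be fitted.
- Some measurements are optional (faecal samples, muscle strength), so complete cases may be fewer. With 120, k = 15 already fails: 1 + 15 + 105 = 121.

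**Step 6, would so many variables arise?** If no protein were associated with pain, 4000 × 0.05 = 200 would pass a 5% screen, but only 4000 × 1.25 × 10⁻⁵ = 0.05 would pass the Bonferroni level. The plan does not say which level defines a significant variable.

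**The case against.** The strongest reply is that the plan never says all pairwise products enter. The closing words of the sentence could mean only the variables' associations with the outcome, and the remark about inter-correlated factors could mean mutual adjustment. This stands as a caution. Interaction terms remain the natural reading, because the same section says the factors are "inter-correlated so investigation of their interaction must be ascertained" and the regression sentence lists interactions in addition to the variables' impact. If something else was meant, the sentence still needs correcting.

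Second, every rate depends on values the plan does not give. This also stands. A reader might infer that a false interaction is more likely than not at five variables. At 0.05 it is not: the figure is 40–49%, and even odds are passed at six. At 0.01 it is about 10–15%. If interactions had to meet 1.25 × 10⁻⁵ the concern would vanish at five variables (10 × 1.25 × 10⁻⁵ = 0.0125%), but Methods does not apply that level to them.

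Third, a reader might infer that the stepwise model will break down. The documents do not show this. At the Bonferroni level, 17 or more variables would need many real or co-varying signals. A model with too many parameters would also be noticed when fitted, so it would force a change of method and would not silently give a wrong answer.

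Fourth, Methods speaks of exploration, and no objective in the Synopsis or in the Primary and Secondary Objectives is an interaction. That lowers the severity. It does not supply the missing rule, since nothing labels interaction results as exploratory.

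**Conclusion.** The point holds as a modest one. As written, the plan searches interactions by backward elimination in 140 people, and its only error level does not count them.

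The size given rests on three assumptions: all pairs enter, k is about five or six, and terms stay at 0.05. Then roughly two in five to one in two analyses with five variables, and more than half with six, would keep at least one interaction that is not real. A looser retention level makes this worse, and a stricter one makes it much smaller.

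The limit of 17 variables is exact for a full two-way model with 140 complete cases, but it is a boundary and not a prediction. Nor do the documents support reading this as a threat to the main conclusions: the signature and association objectives do not depend on an interaction term.

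**What to change.** In Statistics, Methods:

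1. Run the backward stepwise step on main effects only.
2. Then test all pairwise interactions between the retained variables with one block F-test at 5%. In simulations with no real interaction, main-effects selection followed by this test gave a false result in about 2–8% of studies.
3. The block meets the same limit of fit, so state in advance the number of retained variables above which it will not be used. Above that number, test a short list of interactions named beforehand, with Bonferroni over the list.
4. Label any other interaction exploratory.
5. Replace the closing words of the regression sentence by: interactions between the retained independent variables.

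The significance level for the screen and the retention level for main effects are also unstated. They need to be given for the step to be reproducible, and the changes above do not settle them.

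The cost is a few sentences and no new data. The small downside is that single interactions found by searching can no longer be reported as findings.
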